To date, there have been nine transcranial magnetic stimulation studies for the treatment of AUD. Results suggest TMS may serve as a novel treatment intervention for AUD. However, the generalizability of the published clinical trials to Veterans is severely limited because of several design limitations:

- All were international studies with modest sample sizes, did not include Veterans, and consisted primarily of inpatients; AUD treatment at most VA and civilian facilities delivered via outpatient clinics
- Six of nine studies were single blind designs, only five utilized a true sham control condition; double blind, sham/placebo controlled designs are the standard in evaluation of the efficacy of an intervention.
- Six studies excluded participants for conditions e.g., major depressive disorder that commonly co-occur with AUD, and the effects of concurrent smoking on TMS efficacy were not rigorously evaluated. Consequently, the results do not generalize to the typical Veteran seeking treatment for AUD.
- Two studies employed single TMS sessions and four had 10 total sessions; this number of treatments may have not been sufficient to promote sustained abstinence, particularly in Veterans.
- The primary outcome measure in most studies was craving. Higher baseline craving is moderately associated with relapse risk during the first few weeks of treatment, but is a poor predictor of relapse several months after treatment. Therefore, it is necessary to obtain baseline measures of impulse control and risk taking, which are substantially more robust predictors of relapse after treatment.
- The primary follow-up period was 1 month; such a short follow-up interval did not permit evaluation of the long-term efficacy of TMS

Title : Transcranial Magnetic Stimulation for the Treatment of Veterans With Alcohol Use Disorders
Approval Period: 02/28/2025 - 02/28/2026

treatment. Regular monitoring over the entire first 1 year following treatment is imperative, given relapse during the first 6 months-1 year following treatment is strongly related to clinically significant impairments in psychosocial functioning over the ensuing 1-3 years in Veterans and civilians with an AUD.

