Secondary Hypothesis:

In the active rTMS group, Veterans with: (a) lower Glx concentration, (b) lower perfusion (blood flow), and (c) smaller volume of the left DLPFC at baseline will demonstrate a longer duration of abstinence over 6 months post treatment. Confirmation of this hypothesis will indicate that participants who exhibit lower baseline Glx concentration, lower perfusion (blood flow), and/or smaller left DLPFC volume, and receive active rTMS, demonstrate the most robust rTMS treatment response because rTMS addresses these key neurobiological deficits that are associated with increased relapse risk. Confirmation of this hypothesis will advance our understanding of the neurobiological characteristics that predict the greatest benefit from rTMS at entry into treatment for AUD.

Statistical Approach: The Secondary Hypothesis will be tested with generalized linear mixed modeling or linear mixed modeling, depending on the distribution of the dependent measure. Duration of abstinence is the dependent measure. Neuroimaging measure (e.g., Glx level) and treatment group (active rTMS vs. control) are the target predictors, with age as a covariate because it will likely account for significant within and between subject variance [20]. Smoking, PTSD and/or substance use severities will be used as covariates if there are post-hoc differences between treatment groups on these variables after random assignment. We predict an interaction between the specific neuroimaging measure (e.g., Glx level) and treatment group; follow-up simple effect tests will indicate that participants in the active rTMS group with lower Glx concentration, lower perfusion (blood flow), and smaller volume of the left DLPFC at baseline will show the longest duration of abstinence. Separate models will be run for each neuroimaging predictor to minimize the risk of overfitting and corresponding inflated Type I error. To control significance levels of main effects and interactions for multiplicity of tests, we will employ a modified Bonferroni procedure described in our previous studies (see [71] for details).

Exploratory Hypothesis 1

1a) Veterans with co-occurring MDD, who receive active rTMS, demonstrate a significantly lower frequency of relapse over 6 months following treatment than controls (i.e. Veterans with co-occurring MDD who receive sham rTMS).

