Statistical Approach: Exploratory Hypothesis 1a will be tested with binary logistic regression. The criterion/dependent measure is relapse status (abstained or relapsed during the 6 months after last rTMS session). Treatment group (active rTMS vs. control) is the target predictor, with antidepressant use (binary, yes/no) as a covariate. Education and severity of PTSD, substance use, and/or depressive symptomatology will be considered as covariates if, after random assignment, there are post-hoc differences between treatment groups on these variables following breaking of the blind.

1b) Veterans with co-occurring MDD, who receive active rTMS, demonstrate significantly greater duration of abstinence in the 6 months following treatment than controls.

Statistical Approach: Exploratory Hypothesis 1b will be tested with Cox regression. The criterion/dependent measure is duration of abstinence after the final rTMS session. The target predictor and covariates include those for Exploratory Hypothesis 1a.

Exploratory Hypothesis 2

2a) Cigarette smokers, who receive active rTMS, demonstrate a significantly lower frequency of relapse over 6 months following treatment than controls (i.e., Veterans with co-occurring smoking who receive sham rTMS).

Statistical Approach: Exploratory Hypothesis 2a will be tested with binary logistic regression. The criterion/dependent measure is relapse status (abstained or relapsed during the 6 months after last rTMS session). Treatment group (active rTMS vs. control) is the target predictor and with current pharmacotherapy for smoking cessation use (binary, yes/no) as a covariate. Education and severity of PTSD, substance use, and/or smoking severity (based on pack-years) will be considered as covariates if, after random assignment, there are post-hoc differences between treatment groups on these variables following breaking of the blind.

2b) Smokers, who receive active rTMS, demonstrate a significantly greater duration of abstinence over the 6 months following psychosocial treatment than controls.

Statistical Approach: Exploratory Hypothesis 2b will be tested with Cox regression. The criterion/dependent measure is duration of abstinence after final rTMS session. Treatment group is the target predictor and covariates include those for Exploratory Hypothesis 2a.

Tertiary Analyses

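### Exploratory Hypotheses 2a/2b test rTMS among smokers only, with no treatment-by-smoking term, so they cannot estimate whether smoking changes efficacy, a gap the protocol says it will address

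*Combined protocol and SAP*

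**What the plan says.** Background, section 3a, lists limits of the earlier TMS trials in AUD. One item says that six of them left out people with common co-occurring conditions such as major depression, and that "the effects of concurrent smoking on TMS efficacy were not rigorously evaluated". The section closes by saying that this project will deal rigorously with the listed limits.

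In Data Analyses, Exploratory Hypothesis 2a is that "Cigarette smokers, who receive active rTMS, demonstrate a significantly lower frequency of relapse over 6 months following treatment than controls", and the controls are defined as "Veterans with co-occurring smoking who receive sham rTMS". The logistic model is: "Treatment group (active rTMS vs. control) is the target predictor and with current pharmacotherapy for smoking cessation use (binary, yes/no) as a covariate". Education and some severity scores may be added if the arms differ after unblinding. Hypothesis 2b uses Cox regression with the same covariates.

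Exploratory Hypothesis 1a has the same form: "Veterans with co-occurring MDD, who receive active rTMS, demonstrate a significantly lower frequency of relapse over 6 months following treatment than controls", with controls "Veterans with co-occurring MDD who receive sham rTMS". Its model is: "Treatment group (active rTMS vs. control) is the target predictor, with antidepressant use (binary, yes/no) as a covariate". Hypothesis 1b is the Cox counterpart.

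Two other parts of Data Analyses bear on this. The Secondary Hypothesis specifies an interaction between treatment group and each imaging marker. The Tertiary Analyses refer to possible interactions among treatment, neurobiological, neurocognitive and clinical variables in a latent-variable model, but name no smoking or MDD term.

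**The concern.** Whether concurrent smoking affects TMS efficacy is most naturally a question about effect modification: is the active-sham difference in smokers different from that in non-smokers? An analysis that leaves out non-smokers cannot answer it. The smokers-only p-value depends on the effect in smokers and on how many there are. It carries no information about the contrast between the strata.

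At stake is whether the analysis matches a stated purpose. The trial would report an effect in smokers, with less power than the primary analysis, and nothing to compare it with. The same limit applies to MDD if the team wishes to say anything about whether depression changes the response.

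**Working it through.** **Step 1: structure.** The documents give no power, target effect, alpha or subgroup share for these analyses, so there is no stated figure to reproduce. The main check is of the text.

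| Item | Smoking (2a/2b) | MDD (1a/1b) |
|---|---|---|
| Participants compared | active smokers v sham smokers | active MDD v sham MDD |
| Fixed model terms | treatment, smoking-cessation drug | treatment, antidepressant |
| Treatment-by-subgroup term | none | none |
| Gap named in Background 3a | effect of smoking on efficacy | exclusion of such patients |

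The structural point holds for both hypotheses. The mismatch with the Background holds for smoking only.

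**Step 2: inputs for an illustration.** From the documents: 50 per arm (Study Procedures, design paragraph), and relapse within 6 months of at least 60% (Purpose, section 1b), so 60% is used for sham. Assumed: active relapse in smokers 35%, smoker share 40% or 60%, smokers split evenly between arms, two-sided alpha 0.05, no dropout, no covariates.

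**Step 3: power of the active-sham test.** With n per arm, d = |p1 − p2| and p̄ the mean of p1 and p2,

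power = Φ{ (d − 1.96·√[2p̄(1−p̄)/n]) / √[(p1(1−p1) + p2(1−p2))/n] }.

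Here d = 0.25, p̄ = 0.475, p1(1−p1) = 0.24 and p2(1−p2) = 0.2275.

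- All participants, n = 50: (0.25 − 1.96×0.0999)/0.0967 = 0.56, power 71%.
- Smokers at a 60% share, n = 30: (0.25 − 1.96×0.1289)/0.1248 = −0.02, power 49%.
- Smokers at a 40% share, n = 20: (0.25 − 1.96×0.1579)/0.1529 = −0.39, power 35%.

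Over active relapse of 30-40% and shares of 30-70%, power within the subgroup is 19-72%, against 52-87% for the whole trial. With a 60% share and the same effect in everyone, the smokers-only test would still miss significance in about half of trials.

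**Step 4: what each test responds to.** I simulated 400,000 trials per row, with Wald tests on log odds ratios and 0.5 added to each cell. Sham relapse is 60% throughout and active relapse in smokers is 35%.

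| Smoker share | Active relapse in non-smokers | Smokers-only test rejects | Interaction test rejects |
|---|---|---|---|
| 60% | 35% (same effect) | 50% | 4.5% |
| 60% | 60% (no effect) | 51% | 22.5% |
| 60% | 15% (larger effect) | 50% | 16.9% |
| 40% | 35% | 32% | 4.4% |
| 40% | 60% | 32% | 21.8% |
| 40% | 15% | 32% | 21.5% |

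Within each share, the smokers-only column does not change with the effect in non-smokers. The interaction column does, but weakly.

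**Step 5: precision of the interaction.** With n smokers and m non-smokers per arm, the variance of the log ratio of odds ratios is the sum of 1/(n·p(1−p)) over the two smoker cells and 1/(m·p(1−p)) over the two non-smoker cells. For n = 30, m = 20 and no effect in non-smokers:

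1/7.2 + 1/6.825 + 2/4.8 = 0.139 + 0.147 + 0.417 = 0.702, SE 0.838.

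The 95% CI factor is exp(1.96×0.838) = 5.2. The true log ratio is ln(1.5) − ln(0.35/0.65) = 0.405 + 0.619 = 1.025, so power = Φ(1.025/0.838 − 1.96) = 23%. Across the six rows the CI factor is 5.2 to 6.3. Varying active relapse over 30-40% and the share over 30-70%, with no effect outside the subgroup, interaction power is about 15-33%.

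**The case against.** The strongest reply is that the models test exactly what the hypotheses state. Hypothesis 2a claims that active smokers relapse less than sham smokers, and the model tests that. Where the plan wants an interaction, for the imaging markers, it asks for one, so the difference may be deliberate. The Background item that mentions smoking also ends on generalizability, and showing a benefit among smokers is one reasonable answer to that. This stands in part: the tests are valid for the hypotheses as worded. But the clause on smoking concerns its effect on efficacy, and no named analysis estimates that.

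A reader might infer that the MDD tests also miss the protocol's stated gap. The documents do not support this. The complaint about MDD is exclusion, and enrolling these Veterans and comparing active with sham among them addresses it.

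A reader might also infer that the plan ignores interactions with clinical variables altogether. It does not, since the Tertiary Analyses mention them. With no term named and model size restricted by the sample, however, that is not a prespecified estimate for smoking or MDD.

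Finally, the interaction would be badly underpowered. That is correct. It is a reason to report an interval rather than a test result, not a reason to leave the contrast unestimated.

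**Conclusion.** The concern holds in a limited form. Exploratory 2a/2b cannot estimate effect modification by smoking, although Background 3a says that gap will be addressed. Exploratory 1a/1b cannot estimate effect modification by MDD, but the protocol does not promise that they will. This conclusion rests on the text alone. The sizes depend on assumed relapse rates and subgroup shares and are illustrations.

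Two stronger readings go too far. One is that the results will be misreported as smoking-specific or MDD-specific benefit, or as loss of efficacy. Nothing in the documents says so, and the all-participant primary result will stand beside them. The other is that adding the term would settle the question. At 100 participants it would give an interval from the estimate divided by about 5-6 to the estimate multiplied by about 5-6.

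The point is minor: the hypotheses are labelled exploratory and the primary analysis is not affected.

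**What to change.** Amend Exploratory Hypothesis 2 so that the logistic and Cox models are fitted in all randomised participants with treatment, smoking status, treatment × smoking, age and RBANS total score, keeping the planned smoking-cessation-drug covariate. If effect modification by MDD is of interest, do the same for Exploratory Hypothesis 1, keeping antidepressant use.

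Report the treatment effect in both strata, and the ratio of odds ratios (logistic) or hazard ratios (Cox) with its 95% CI, labelled exploratory. Keep the within-subgroup tests as descriptive. State that no claim of subgroup-specific benefit or loss of efficacy will rest on a subgroup p-value alone.

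The cost is SAP wording and a few model runs, with no new data or visits. The drawbacks are a wide and probably inconclusive interval, and a fuller model: six terms, against about 48 relapses if rates are 60% and 35% overall (50×0.60 + 50×0.35 = 47.5).
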